
2.1 Objectives & Hypotheses
	
Disturbed sleep is one of the most common and distressing responses to exposure to severe trauma and can persist in many of those affected with and without accompanying posttraumatic stress disorder (PTSD). Insomnia is a risk factor for many of the conditions that are prevalent in trauma-exposed populations including PTSD, depression, and physical health conditions such as obesity, and cardiovascular disease. Trauma-related insomnia (TRI) is not typically differentiated in studies characterizing insomnia and its treatment, and insomnia accompanying PTSD has been shown to be relatively refractory to the treatments that are established for PTSD. Thus treatment of TRI presents an unmet need that has implications for the large and growing groups of people exposed to trauma in terms of relieving distress and preventing further psychiatric and medical morbidity.
 
Most of the data on TRI comes from research on populations with PTSD. Difficulty initiating and maintaining sleep is designated as one of the heightened arousal symptoms of PTSD in the DSM. Sleep studies have suggested reduced slow wave sleep (SWS) in some PTSD populations and fragmented rapid eye movement (REM) sleep when PTSD is developing, and during its more acute stages. Suvorexant is a first in class orexin antagonist and is approved by the FDA for the indication of insomnia. Orexin antagonists dampen the activity of a specific arousal enhancing system in the brain during sleep. In rodent models suvorexant has been shown to enhance, and in healthy humans, to not affect slow wave and REM activity (in contrast with traditional hypnotics which can diminish both). Reducing arousal during sleep while maintaining REM and slow wave sleep is a promising profile for the treatment of TRI. We are therefore proposing a placebo controlled evaluation to assess the efficacy of suvorexant for treating TRI with and without PTSD and its tolerability in these populations. We will include polysomnography (PSG) in order to probe potential mechanisms and biomarkers predicting response. The proposed study will meet the objectives below and test the following hypotheses:
 
Objective 1. To recruit a group of participants that meet criteria for insomnia and who identify a severely threatening event (DSM criterion A trauma) as a precipitant or a factor that significantly exacerbated their sleep disturbance; and to determine the frequency of PTSD diagnoses and symptoms among the recruited participants.
 
Hypothesis 1) – Recruitment will reveal TRI to be a common condition that in approximately half of cases occurs absent PTSD.
 
Objective 2. To evaluate the effectiveness and tolerability of suvorexant on insomnia and when present, associated PTSD symptoms and its effects on PSG measures in participants with TRI.
 
Hypothesis 2a) Insomnia will improve, and nightmares and other PTSD symptoms will be reduced with suvorexant treatment compared with placebo.
 
2b) Improved sleep will be associated with reduced non-sleep related PTSD symptoms when present.

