2.7 Statistical Analysis and Sample Size Justification	
The data will be analyzed by the Investigator and Co-investigator.
 
Main outcomes will be ISI, CAPS nightmare frequency and total score, diary and PSG sleep latency and WASO at week 3 and for non-PSG variables Med week 6. We will also explore effects on REM and SWS and their relationships to other study outcomes.
 
An alpha level of .05 (one-tailed) will be applied in testing Hypotheses 2a), 2b), 2d), and 2e). Initially, data will be pre-screened for errors, outliers, normality of distributions, and any necessary modifications, such as transformation of variables and/or elimination of cases, will be conducted.
 
Our initial objectives are descriptive. We will generate frequencies of types of trauma exposures associated with insomnia and the rates for PTSD diagnoses and sub-diagnostic threshold PTSD symptoms in the recruited study population (Objective 1) and the frequency of adverse events (Objective 2). The latter will be descriptively contrasted to the extant data for suvorexant from the insomnia registry trials as a guide to planning future trials including dosing.
 
Hypothesis 2a) Insomnia will improve, and nightmares and other PTSD symptoms will be reduced with suvorexant treatment compared with placebo: We will compare baseline characteristics of the treatment groups using independent samples t-tests for continuous variables or chi-square tests for categorical variables. If a significant group difference is found in some of the variables, the variable(s) will be included in subsequent analyses as a covariate(s). We will perform 2 (Group) x 3 (Time: baseline, Med week 3, and week 6) mixed ANOVAs or ANCOVAs [if there is a covariate(s)] to compare the changes in ISI scores, nightmare frequency, and CAPS scores, separately, between the two groups.
 
Hypothesis 2b) Improved sleep will be associated with reduced non-sleep PTSD symptoms: Correlation coefficients between baseline – Med week 6 changes in sleep measures (e.g., ISI scores and nightmare frequency) and changes in the CAPS scores excluding two sleep-related items will be computed. In addition, we will exploratively examine if there is an interaction with treatment condition by performing regression analyses in which CAPS scores will be predicted by changes in sleep measures, treatment condition, and a Sleep measure X Treatment condition interaction.
 
Hypothesis 2d) Sleep latency and wake after sleep onset (WASO) will be reduced with suvorexant treatment compared with placebo: We will perform 2 (Group: suvorexant vs. placebo) x 2 (Time: Baseline and Med week 3) mixed ANOVAs or ANCOVAs [if there is a covariate(s)] to compare the changes in PSG measured sleep latency and WASO between the suvorexant and placebo groups.
 
Exploratory hypothesis 2e) When reduced at baseline (i.e., SWS below 100 minutes and mean REM segment duration below 15

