
	
minutes), SWS and the duration of continuous segments of REM sleep will increase with suvorexant than placebo: Participants with reduced baseline SWS (below vs. above 100 minutes) and mean REM segment duration (below vs. above 15 minutes) will be included in the analyses. 2 (Group) x 2 (Time: Baseline and Med week 3) mixed ANOVAs or ANCOVAs will be performed to compare treatment changes in SWS and REM segment duration between the suvorexant and placebo groups.
 
Power Considerations:
 
G*Power 3.1 ³³ was used to conduct power analysis.
 
Power analysis for Hypothesis 2a) is based on the effect size estimated using findings of Herring and colleagues' ²² placebo controlled trial of suvorexant in adults with insomnia. Since there are no data for suvorexant on trauma related nightmares and PTSD symptoms, we also used Taylor and colleagues' ²⁴ placebo controlled trial of prazosin in civilian outpatients with PTSD, sleep disturbances, and nightmares. Taylor et al. found a large-size effect of prazosin on changes in trauma-related nightmare severity compared with placebo ($d = 0.96$ or $f = 0.48$) and PTSD severity ($d = 0.79$ or $f = 0.40$) and a medium-size effect on changes in trauma-related insomnia symptoms severity ($d = 0.50$ or $f = .25$). Herring and colleagues found a small-size effect of a 1-month suvorexant treatment (20mg for nonelderly and 15mg for elderly) on insomnia severity measured by the ISI ($d = 0.39$ or $f = 0.20$). To detect an $f = 0.20$ Group x Time interaction effect in the proposed mixed ANOVA with 80% power, a total of 42 participants are needed.
 
Power analysis for Hypothesis 2b) is based on the effect sizes estimated using Krakow and colleagues' findings ³⁴ from their study examining effects of cognitive behavioral therapy for nightmares and insomnia in crime victims with PTSD. They found correlations between changes in nightmare frequency, insomnia severity, and sleep quality and changes in overall PTSD symptom severity ranging from $r = .37$ to $.40$. A sample size of 43 will allow for detecting similar size effects with 80% power.
 
Power analysis for Hypothesis 2d) is based on findings from the aforementioned Herring and colleagues' study. They found that effects of suvorexant on sleep latency and WASO were $f = 0.17$ and 0.31, respectively. To detect an effect size of 0.17 using the proposed mixed ANOVA with 80% power, a total of 70 participants are needed.
 
Power analysis for Exploratory hypothesis 2e) is based on findings from the aforementioned Taylor and colleagues' study. They found that the effect of prazosin on mean REM period duration was $f = 0.50$. Using the proposed mixed ANOVA, a total of 16 participants will allow for detecting a large size within-between interaction effect ($f = 0.50$) with 80% power.

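### Hypothesis 2a applies a one-tailed .05 to a 2-df Group x Time F test that has no direction, and the seven main outcomes have no primary and no multiplicity rule

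*Combined protocol and SAP*

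**What the plan says.** Section 2.7 sets one error rate for four hypotheses: "An alpha level of .05 (one-tailed) will be applied in testing Hypotheses 2a), 2b), 2d), and 2e".

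Hypothesis 2a is directional: "Insomnia will improve, and nightmares and other PTSD symptoms will be reduced with suvorexant treatment compared with placebo". For its test the plan says: "We will perform 2 (Group) x 3 (Time: baseline, Med week 3, and week 6) mixed ANOVAs or ANCOVAs", the purpose being "to compare the changes in ISI scores, nightmare frequency, and CAPS scores, separately, between the two groups". The power paragraph confirms that the interaction is the test of interest: "Group x Time interaction effect in the proposed mixed ANOVA with 80% power, a total of 42 participants are needed".

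Hypothesis 2d uses a 2 x 2 mixed ANOVA "to compare the changes in PSG measured sleep latency and WASO between the suvorexant and placebo groups", and its sizing statement reads: "To detect an effect size of 0.17 using the proposed mixed ANOVA with 80% power, a total of 70 participants are needed".

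The outcome list opens: "Main outcomes will be ISI, CAPS nightmare frequency and total score, diary and PSG sleep latency and WASO at week 3", and the non-PSG variables are added at week 6. That makes seven outcomes: ISI, CAPS nightmare frequency, CAPS total, diary sleep latency, diary WASO, PSG sleep latency and PSG WASO. The documents name no primary outcome, testing order or multiplicity adjustment. They give no contrast or follow-up comparison for reading direction from the 2a interaction. Diary latency and diary WASO have no stated between-group test.

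**The concern.** There are two separate faults.

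**The 2a rule is not defined.** A 2 x 3 interaction has (2 - 1)(3 - 1) = 2 numerator df. It rejects when the group difference changes over the three visits in any pattern, including patterns that favour placebo. A one-tailed level has no standard meaning for such a test. One analyst might use F at .05, another F at .10, and a third F at .10 with a check on the sign at some visit. None of these is a test that suvorexant is better at a stated visit. The problem is confined to 2a: the 1-df tests in 2d and 2e and the correlations in 2b can be one-tailed.

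**There is no primary outcome.** Five outcomes have a named group comparison, each tested separately at the full level. Any one of them could be presented as the trial's efficacy result, and the plan does not say which one counts.

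**Working it through.** **Inputs from section 2.7.** f = 0.20 (d = 0.39) and N = 42 for 2a; f = 0.17 and N = 70 for 2d; 80% power for both. Section 2.5 expects 70 retained.

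**Assumptions, because the plan gives none.** Equal arms (35 each), repeated-measures correlation ρ = .5 unless stated, sphericity.

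**1. The plan's own sample sizes.** For the interaction, λ = f²·N·m/(1 - ρ), df1 = m - 1, df2 = (N - 2)(m - 1), with m visits.
- 2a: λ = 0.04 × 42 × 3/0.5 = 10.08. Power of F at .05 is 80.3%, so 42 is reproduced.
- 2d: λ = 0.0289 × 70 × 2/0.5 = 8.09. Power of F at .05 is 80.1%, so 70 is reproduced.
- The inputs are not identified by this match. The pairs alpha/ρ = .05/.5, .10/.37 and .025/.60 all return both 42 and 70. At ρ = .5, reading one-tailed .05 as F at .10 would give 34 and 56.

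**2. Does a significant 2a F carry direction?** In null simulations at 35 per arm, about 5% of 2a tests reject. The rejections split into rough thirds: suvorexant better at both visits, placebo better at both, and mixed (33%, 35% and 32% in one run).

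**3. Does it identify the visit?** Write the group difference at baseline, week 3 and week 6 as a vector. Under the assumptions above, λ is proportional to the sum of squared deviations from the vector's mean.
- Lasting effect (0, d, d): mean 2d/3, sum = (4/9 + 1/9 + 1/9)d² = 2d²/3.
- Week-3-only effect (0, d, 0): mean d/3, sum = (1/9 + 4/9 + 1/9)d² = 2d²/3.

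The two are identical, so the omnibus test has the same power for either pattern.

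**4. Per-test error for 2a.** Simulated null rejection at ρ = .3/.5/.7:

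| Reading of the rule | Rejection rate |
|---|---|
| F at .05 | 5.2/5.0/5.1% |
| F at .10, week-6 sign required | 5.1/4.9/5.0% |
| F at .10, no sign check | 10.1/10.0/10.1% |

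**5. Error across the five named comparisons.** Take the three 2a tests as F at .05, counted as favouring suvorexant only if the week-6 change does (about .025 each). Take the two 2d tests as one-sided at .05. If the outcomes are independent:
- at least one result favouring suvorexant: 1 - 0.975³ × 0.95² = 16.4%;
- at least one rejection of either kind: 1 - 0.95⁵ = 22.6%.

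Simulation with correlated outcomes:

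| Outcome correlation | Favouring suvorexant | Any rejection |
|---|---|---|
| 0 | 16% | 23% |
| .3 | 15% | 21% |
| .5 | 14% | 20% |
| .7 | 12% | 17% |

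**6. Which repair does what?** Replacing the five tests with five one-sided 1-df contrasts, still with no primary, gives 23/20/19/17% favouring suvorexant at the same outcome correlations. Changing the form of the test therefore does not control family-wise error. Naming one primary does, because a single test at .05 then carries the claim.

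**The case against.** **The group means will show direction.** They will, but only descriptively; the plan attaches no rule to them.

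**One-tailed .05 on the F doubles the error.** A reader might infer this, but the documents do not support it. It is true only if the p-value is halved with no check of sign, which the plan neither states nor excludes. The other two readings in step 4 hold about 5%.

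**The trial is too small for ISI.** A reader might infer this too. If d = 0.39 is taken as a raw-score group difference present at both treatment visits, the planned omnibus has 27/37/57% power at N = 70 (ρ = .3/.5/.7). That pattern corresponds to an interaction f of 0.39/√18 = 0.092, not 0.20; reaching f = 0.20 would need d = 0.20 × √18 = 0.85. With the plan's f = 0.20 entered directly, power is 80% at 42 and about 96% at 70 (ρ = .5). The plan does not say in what SD units d is expressed or how it maps onto the interaction. No sizing error is established here; what is missing is a stated definition.

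**Week 6 need not be the decisive visit.** This stands. The plan makes both weeks 3 and 6 outcome times, 2a claims no durability, and nothing in the documents predicts that an effect would fade. The week-3-only pattern shows only what the F cannot distinguish.

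**The study is largely descriptive.** Section 2.7 calls its initial objectives descriptive, but 2a and 2d are efficacy hypotheses with 80% power calculations. Only 2e and one regression within 2b are labelled exploratory.

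**Conclusion.** Both faults hold as the plan is written. The one-tailed level for 2a is undefined, and a significant 2a interaction does not establish that suvorexant is better or at which visit. This part is about the decision rule and interpretation, and adds no per-test error under either sensible reading. The absence of a primary outcome and a multiplicity rule is what inflates error: about 12% to 16% for at least one chance result favouring suvorexant, and 17% to 23% for any rejection, against a nominal 5%. Those ranges assume 35 per arm, a repeated-measures correlation of .5, outcome correlations from .7 down to 0, and 2a read as F at .05. The fault in the 2a rule needs no numerical assumption. The matter should be settled before unblinding, because a primary outcome chosen after results are seen does not control error.

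**What to change.** Amend section 2.7 before unblinding:

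1. The sponsor names one primary outcome and visit from those the plan already powers, for example ISI at a stated visit or PSG sleep latency at week 3.
2. Test it with a 1-df baseline-adjusted suvorexant-minus-placebo contrast, with a confidence interval and stated sidedness.
3. Keep one-tailed alpha for 1-df tests and correlations only, with 2d and 2e written as signed t tests. Declare any retained 2 x 3 F non-directional at .05.
4. Give diary latency and diary WASO the same group contrast, so that all seven main outcomes have a defined test.
5. Make the other six secondary, either Holm-adjusted or reported with confidence intervals and no stand-alone efficacy claim.
6. State the power of the chosen contrast at N = 70 with its alpha, tails, repeated-measures correlation and effect-size definition, and give the same inputs for 42 and 70.

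Item 6 matters because the answer depends on the definition. For ISI, entering f = 0.20 in a 1-df change contrast at ρ = .5 needs 42 (one-sided) or 52 (two-sided), both within 70. Reading d = 0.39 as a raw-score difference at week 6 gives 51/58/73% one-sided or 38/45/61% two-sided power at 70 (ρ = .3/.5/.7).

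The cost is wording only, with no new visits or data. The downside is that the non-primary main outcomes lose stand-alone claim status and one disclosed test carries the efficacy claim.

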
	
2c) Suvorexant will be well tolerated by the participants.
 
2d) Sleep latency and wake after sleep onset (WASO) will be reduced with suvorexant treatment compared with placebo.
 
2e) (exploratory hypothesis) When reduced at baseline (i.e. SWS below 100 minutes and mean REM segment duration below 15 minutes) SWS and the duration of continuous segments of REM sleep will increase with suvorexant compared with placebo.

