these data we predict that suvorexant will not precipitate REM sleep-related parasomnias in the proposed target population but rather will consolidate fragmented REM sleep periods that have been observed in the earlier stages of PTSD. This would be similar to the effects seen for the alpha 1 adrenergic antagonist prazosin, an agent that targets central noradrenergic arousal promoting mechanisms and has been shown to reduce the severity of nightmares and related sleep disruption with PTSD. Specifically, the only study that monitored EEG sleep found lengthened discreet REM sleep periods with increases in the amount of REM sleep that were proportionate to the increases in overall sleep time. Prazosin, however, did not reduce time to fall asleep in this study.²⁴ Given the data from animals and that the absence of changes was in healthy volunteers, we hypothesize that suvorexant will also enhance SWS when it is deficient at baseline.

Summary of Significance

Insomnia is quite common among those exposed to trauma. PTSD usually features insomnia symptoms and insomnia precipitated or exacerbated by trauma is also common absent a PTSD diagnosis. TRI does not appear to respond well to previously available treatments. Fragmented patterns of REM sleep have been observed during the development of PTSD and within several years of its onset. Suvorexant is promising for maintaining overall sleep and REM sleep that is being disrupted by heightened arousal. In addition to proposing a placebo-controlled evaluation of efficacy and tolerability of suvorexant for TRI we further propose utilizing PSG to potentially elucidate physiological biomarkers of treatment response. Given the rising toll of trauma this proposal is a timely response to Merck's call for proposals for "clinical studies exploring the investigational use of suvorexant in key insomnia subpopulations."

2.3 Study Design	A double-blind placebo-controlled 6-week trial of suvorexant 10 – 20mg for trauma related insomnia (with and without PTSD) with polysomnography								
-------------------------	---	--	--	--	--	--	--	--	--

2.4 Study Flowchart	(Visits)	Prescreen	Screen	Baseline	Med Week 1	Med Week 2	Med Week 3	Med Week 6	Post-Rx Week1
	Phone screen	X							
	Physical		X						
	Wt. & Vital Signs		X		X	X	X	X	X
	DSISSD and SCID		X						
	LEC		X						
	CAPS			X			X	X	
	ISI			X			X	X	X
	Sleep Diaries			X (1 week)	X		X	X	X(1week)
	PSG			XX			X		
	AE				X	X	X	X	X

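### Hypothesis 2c (good tolerability) is listed for testing, but section 2.7 supports it only with adverse-event frequencies set against earlier trials, which in about 45 treated people cannot carry that conclusion

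*Combined protocol and SAP*

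**What the plan says.** Section 2.1 introduces its list with "The proposed study will meet the objectives below and test the following hypotheses". One item is "2c) Suvorexant will be well tolerated by the participants". No rate, margin or criterion is attached to it, and Objective 2 names tolerability alongside effectiveness.

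Section 2.7 gives the significance level as follows: "An alpha level of .05 (one-tailed) will be applied in testing Hypotheses 2a), 2b), 2d), and 2e"). Hypothesis 2c is not in that list. Adverse events appear in the paragraph on descriptive aims, where the planned output is "the frequency of adverse events (Objective 2"). The next sentence says "The latter will be descriptively contrasted to the extant data for suvorexant from the insomnia registry trials", to help plan later trials, including their dosing. No confidence interval, upper bound or between-arm safety comparison is named, and the power section sizes 2a, 2b, 2d and 2e but not 2c.

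Data collection is thorough. Section 2.5 plans active questioning at each medication visit about common adverse effects, the events of interest from the earlier trials, and parasomnia or narcolepsy-like phenomena, plus a sleepiness questionnaire.

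**The concern.** A directional statement about tolerability is put forward as a hypothesis, but the analysis attached to it yields only percentages from a small group. Low or familiar-looking percentages will tend to be read as support for 2c, although a small sample often produces them even when the true rate is materially higher. Without an interval, the reader cannot see how little has been excluded. The trial has a randomised, blinded placebo arm, but the only contrast stated for adverse events is with other trials in people with a primary insomnia diagnosis. What is at stake is the tolerability conclusion in a trauma-exposed population and its use in planning later trials. No efficacy result is affected.

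**Working it through.** **Inputs from the documents.**
- Sample: 90 recruited, 70 expected to be retained (section 2.5).
- Cited rate of stopping suvorexant for adverse effects: 3% (section 2.2).
- Cited somnolence: 7% on suvorexant, 4% on placebo (section 2.2).

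**Assumption.** The allocation ratio is not stated. I take 1:1, so 90/2 = 45 people start suvorexant and 70/2 = 35 are retained on it. Adverse events are queried at weeks 1, 2, 3 and 6, so people who leave early still contribute data. Forty-five is therefore the natural denominator, and 35 is the pessimistic case.

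**The plan's own figure.** The documents give no precision figure for adverse events. The sample comes from Hypothesis 2d: f = 0.17, 2 groups by 2 times, F-test alpha 0.05, and an assumed correlation of 0.5 between repeated measures. The noncentrality is N × f² × 2/(1 − 0.5). At N = 70 this is 70 × 0.0289 × 4 = 8.09 on 1 and 68 degrees of freedom, giving power 0.801. N = 70 reproduces, and 70/(1 − 0.2222) = 90. Nothing in that calculation concerns safety.

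**Step 1. Event never seen on suvorexant.** The exact one-sided 95% upper bound solves (1 − p)^n = 0.05, so p = 1 − 0.05^(1/n).
- n = 45: 6.4%
- n = 35: 8.2%

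The corresponding upper limits of a two-sided 95% interval, 1 − 0.025^(1/n), are 7.9% and 10.0%.

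**Step 2. How easily zero arises.** The chance of no events is (1 − p)^n. For an illustrative true rate of 2% it is 0.98^45 = 0.40 or 0.98^35 = 0.49.

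**Step 3. One discontinuation for adverse effects.** The observed rate is 1/45 = 2.2% or 1/35 = 2.9%, which looks like the cited 3%. The exact one-sided 95% upper bound solves (1 − p)^n + n p (1 − p)^(n−1) = 0.05.
- n = 45: p = 10.1% (terms 0.008 + 0.042)
- n = 35: p = 12.9% (terms 0.008 + 0.042)

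These bounds are 10.1/3 = 3.4 and 12.9/3 = 4.3 times the cited rate.

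**Step 4. The same outcome under a doubled rate.** If the true rate were 6%, the chance of at most one discontinuation is 0.94^n + n × 0.06 × 0.94^(n−1).
- n = 45: 0.062 + 0.177 = 0.24
- n = 35: 0.115 + 0.256 = 0.37

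**Step 5. Precision of the placebo contrast, if it were reported.** With equal counts of 2 and 2, the Newcombe 95% interval for the difference is ±10.9 percentage points at 45 per arm and ±13.5 at 35 per arm. Equal counts would still leave a sizeable excess open, so the interval has to be shown.

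**The case against.** The strongest reply is that the plan never makes a safety inference. Section 2.7 labels these aims descriptive, leaves 2c out of the alpha statement, and uses the external contrast only to guide later trials. A reader might infer that the plan treats the absence of an observed excess as proof of safety. No such rule is written, and that reading should be dropped. The reply lowers the severity but does not remove the mismatch, because 2c is still listed for testing and has nothing that could support it. An interval fits a descriptive analysis and needs neither a test nor power.

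Two other stronger readings also fail.
- One might say that the background prediction, "we predict that suvorexant will not precipitate REM sleep-related parasomnias in the proposed target population", rests on this trial's event counts. It does not. Section 2.2 derives it from earlier data, and it can stand as a prior expectation. Only the reporting of parasomnias in this trial needs a bound.
- One might size the problem by how often a comparison with placebo would miss an excess. Section 2.7 plans no such comparison, so those miss rates do not describe the plan. Under the contrast it does plan, a true somnolence rate of 14% against the cited 7% would give an observed rate at or below 7% in only about 11% of trials (at most 3 of 45, or 2 of 35). Commoner events are therefore less exposed than rare ones. With 3 of 45 observed (6.7%), the one-sided upper bound is 16.3%, about 2.3 times the cited 7%.

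The documents give no pivotal-trial rate for parasomnias, so no multiple can be stated for them.

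**Conclusion.** The concern holds in a limited form. Hypothesis 2c is stated as something to be tested, while section 2.7 offers only event frequencies and an informal external contrast, with no interval and no stated use of the placebo arm. On that basis "Suvorexant will be well tolerated by the participants" cannot be concluded. Zero events leaves true rates up to 6.4% open (8.2% if only completers count). One discontinuation for adverse effects leaves up to 10.1% open (12.9%).

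These figures rest on 1:1 allocation, which the documents do not state, and on the planned recruitment being met. The 2%, 6% and 14% rates are illustrations, since the documents set no margin for unacceptable harm. The point bears on how tolerability is reported and worded. Sample size, data collection and the efficacy analyses are unaffected.

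**What to change.** In section 2.7, replace the frequency-only statement with an estimation plan.

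1. Tabulate adverse events by arm among all who took study drug.
2. For each queried event, each pre-specified event of interest (parasomnias included) and discontinuation for adverse effects, give the suvorexant rate with an exact 95% upper bound, also when the count is zero. State whether the bound is one- or two-sided.
3. Give the suvorexant-minus-placebo difference with an exact or score 95% confidence interval.
4. Keep the contrast with the earlier suvorexant trials as secondary.
5. Restate 2c as an estimation objective. Word its conclusion as the rates and differences the data exclude, and do not infer good tolerability from low or similar counts. With no margin set, 2c would not pass or fail, and the text should say so.

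The background parasomnia prediction needs no rewording. The cost is a few sentences and some extra table columns from data already collected, with no added participants or visits. The downside is a less favourable tolerability statement.
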